### 2.3.1 Risk Assessment

There are no identified or potential risks of particular severity anticipated based on toxicological data with SUPLEXA in animals, nor based on the mechanism of action and composition (an autologous population of NK and  $\gamma\delta$  T cells, CD8-positive and CD4-positive cells). Additionally, these cellular components have individually been evaluated in clinical studies and found to be well tolerated based on the lack of SAE (Section 2.2).

SUPLEXA is a first-in-class non-engineered autologous cell therapy. This study is ongoing and as of Sept 19 2022, more than 15 subjects were enroled in the study and received from 3 to 6 doses of SUPLEXA. No treatment-related SAE or adverse events had been reported.

Although nothing has been observed to date in blood chemistry, urinalysis, hematological or any labs, nor in any reported AE/SAE, potential risks based on the ongoing study and theoretical concerns that may be associated are presented below (Table 1) based on studies involving the autologous administration of CTL (Ohtani, 2014), CAR-T (Shivani, 2018) and dendritic cells

(Anguille, 2014) as well as the allogeneic administration of NK cells (Kyle B. Lupo, 2019), and  $\gamma\delta$  T cells (Pauza, 2018).

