### 3 OBJECTIVES AND ENDPOINTS

Objectives	Endpoints
Primary	

 
To assess safety and tolerability of SUPLEXA in subjects with malignant solid tumour and haematologic malignancies.
 
	
 
Incidence of dose limiting toxicities (DLTs) (as described in Section 6.5.1).
 
Incidence of adverse events (AEs), and serious adverse events (SAEs) overall, by severity, by relationship to each study intervention, and those that led to discontinuation of study intervention.
 

Secondary 
 
Solid tumours cohort: To assess the efficacy of SUPLEXA in subjects with malignant solid tumour as assessed by the Investigator based on response evaluation criteria in solid tumours (RECIST) v1.1 or by changes in tumour-derived blood biomarkers.
 
Haematologic malignancies cohort: To assess the efficacy of SUPLEXA in subjects with haematologic malignancies (multiple myeloma, lymphoma, and chronic lymphocytic leukemia).
 
	
 
Objective response rate (ORR) defined as the proportion of subjects with best overall response (BOCR) of either a complete response (CR) or partial response (PR).
 
Time to Progression (TTP).
 
Objective response rate as defined by standard of care.
 

Exploratory 
 
Exploratory efficacy outcomes
 
	
 
Duration of Response (DOR)
 
Time to Response (TTR)
 
Clinical Benefit Rate (CBR) defined as CR + PR + stable disease (SD).
 
Progression-free Survival (PFS).
 
Overall Survival (OS).
 
Solid tumours cohort: Change in plasma biomarkers.
 
Haematologic malignancies cohort: Response-relationship with correlative biomarkers in blood and bone marrow including immunophenotyping of circulating PBMC and/or bone marrow, gene expression, mutational analysis.
 

Objectives	Endpoints

 
• To evaluate anti-tumor activity of SUPLEXA by based on modified RECIST v1.1 for immune based therapeutics (iRECIST)
 
	
 
• iORR
 
• iPFS
 
• iDOR
 
• iDCR
 

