#### **4.3 DOSE JUSTIFICATION FOR SUPLEXA THERAPEUTIC CELL DOSE**

The initial cumulative dose selected for this study was based entirely on preclinical mouse xenograft studies in which we dosed mice at ~28x the intended human regimen 3 clinical doses with an option to extend to 6 doses, with each dose approximately 2.5 B cells (range 1.9-3.9 B cells). Given the complete absence of treatment related adverse events for SUPLEXA in the ongoing human study, we propose that after the first 3 doses, administration of up to 14 additional treatments of 5B cells every 2 weeks will be well tolerated, and the actual number of doses depends on the SUPLEXA manufacturing yields for each of 2 patient-specific SUPLEXA batches.

The DSMB will provide an additional review of all safety data and predetermined points in the progress of the clinical study.

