#### 9.3.1 General

Statistical analyses will be performed using SAS® v9.4 or higher (SAS Institute, Cary NC, USA) and all analysis will be described in the SAP finalized before database lock.

The standard summary statistics for continuous variables are sample size (n), mean, standard deviation (SD), median, minimum, and maximum. The standard summary statistics for categorical variables are frequencies and percentages. Time to event variables will be summarized using the Kaplan-Meier method. Where confidence limits are appropriate, the confidence level will be 95% (two-sided), unless otherwise stated.

Individual data (including relevant derived variables) will be presented by parameter in listings. Results of statistical analyses, descriptive summary statistics and supportive listings will also be presented.

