### 9.3.2 Efficacy Analysis

#### Solid Tumour Cohort

The secondary endpoint of ORR will be defined as the proportion of subjects with BOCR of either a CR or PR as assessed by the Investigator using RECIST v1.1 in the Response Evaluable Population as both unconfirmed or confirmed status. ORR will be reported as a proportion along with the corresponding 2-sided 95% Clopper-Pearson exact CI.

A sensitivity analysis of the primary endpoint will be performed in the Response Evaluable Population.

Other secondary and exploratory endpoints are defined as follows for the whole cohort or analysed by tumour type:

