#### **9.3.3 Safety and Tolerability Analysis**

Safety outcomes will be analysed at the end of each study intervention period as well as over the course of the entire study.

The safety assessment will be based on the frequency of adverse events, on the observation of clinically significant abnormalities of laboratory values, concomitant medication use, vital signs, and physical examination data in the Safety analysis set.

Adverse events: Overall AE as well as AE classified by system organ class and preferred terminology according to the Medical Dictionary for Regulatory Activities (MedDRA) will be summarized. Additionally, AE will be summarized by severity and relation to study intervention. SAEs and AEs leading to discontinuation will also be summarized.

Other safety data: These data will be summarized by presenting the proportions of subjects with clinically significant abnormalities or changes from baseline values. Laboratory data will be presented in data listings and summarized.

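### The primary safety endpoints have no planned measure of uncertainty, and the protocol already reasons from a zero count without stating its upper limit

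*Combined protocol and SAP*

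**What the plan says.** Section 3 has one primary objective, safety and tolerability. Its endpoints are "Incidence of dose limiting toxicities (DLTs) (as described in Section 6.5.1") and the incidence of AEs and SAEs, including those leading to discontinuation.

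For the analysis, Section 9.3.3 states "The safety assessment will be based on the frequency of adverse events", together with laboratory, vital sign, physical examination and concomitant medication data in the Safety Analysis Set. AEs are broken down by MedDRA class and term, severity and relationship, and SAEs and discontinuations are summarised. The section contains no interval and does not mention DLTs. The general rule in Section 9.3.1 is "The standard summary statistics for categorical variables are frequencies and percentages". On intervals it says only "Where confidence limits are appropriate, the confidence level will be 95% (two-sided), unless otherwise stated".

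Efficacy is treated differently. In Section 9.3.2, "ORR will be reported as a proportion along with the corresponding 2-sided 95% Clopper-Pearson exact CI". The clinical benefit rate is handled in a similar way, and Kaplan-Meier percentiles get confidence intervals.

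Section 2.3.1 reports that, at the September 2022 cut-off, "more than 15 subjects were enroled in the study and received from 3 to 6 doses of SUPLEXA", and adds: "No treatment-related SAE or adverse events had been reported". Section 4.3 builds on this: "Given the complete absence of treatment related adverse events for SUPLEXA in the ongoing human study, we propose that after the first 3 doses", up to 14 further treatments of 5 billion cells every two weeks will be tolerated well.

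**The concern.** A zero count in a small sample is compatible with a real event rate, and how large a rate depends on the denominator. The plan attaches an exact interval to a secondary proportion and nothing comparable to the primary ones. Sections 2.3.1 and 4.3 show the consequence: a zero count, given without an exact denominator or a bound, becomes the stated human evidence for tolerability of an extended regimen. If the final report follows the same pattern, readers will see percentages without being told what rates the data leave open.

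The DLT endpoint has a further problem. No analysis is named for it, and the population defined for it in Section 9.2 cannot serve as a denominator. An instruction to put an interval on the DLT incidence could not be carried out until that is corrected.

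**Working it through.** The documents state no upper limit, detection probability or safety precision, so there is no planned figure to reproduce.

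**Inputs**
- Related events to date: 0 (Section 2.3.1). Zero related AEs of any kind implies zero related Grade 3 or higher AEs and zero related SAEs, so one limit serves for each.
- Subjects behind that statement: the exact number is not given, only that it exceeds 15. Assumed 16, the minimum, with 20 as a sensitivity value.
- DLT-assessed subjects: 15 (Sections 4.1.2.1 and 6.5).
- Planned total: about 60 (Section 9.1).
- Interval: two-sided 95% Clopper-Pearson, the level in Section 9.3.1 and the method in Section 9.3.2.

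**Formulas**
- Exact upper limit for 0 events in n subjects: 1 − 0.025^(1/n).
- Probability of seeing no events at true rate p: (1 − p)^n.

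| n | What it represents | Upper limit for 0/n | P(no events), true rate 5% | P(no events), true rate 10% |
|---|---|---|---|---|
| 15 | DLT-assessed subjects | 1 − 0.025^(1/15) = 21.8% | 46.3% | 20.6% |
| 16 | Interim statement, minimum n | 1 − 0.025^(1/16) = 20.6% | 44.0% | 18.5% |
| 20 | Interim statement, larger n | 1 − 0.025^(1/20) = 16.8% | 35.9% | 12.2% |
| 60 | Final AE analysis, all event-free | 1 − 0.025^(1/60) = 6.0% | 4.6% | 0.2% |

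With one-sided 95% limits, 1 − 0.05^(1/n), the first three rows become 18.1%, 17.1% and 13.9%. An upper limit of 10% or less at the two-sided level needs n ≥ ln(0.025)/ln(0.90) = 35.01, that is 36 event-free subjects.

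**DLT denominator.** Section 9.2 restricts the DLT evaluable population to dosed subjects who have had a DLT. With d such subjects the incidence in that set is d/d = 100% for any d ≥ 1, and 0/0 for d = 0. No interval can be formed from either. The value of 15 used above comes from the assessment plan, not from Section 9.2. Section 6.5 also opens by tying the DLT definition to the first 3 subjects in each cohort. If only those 6 counted, the limit for 0/6 would be 1 − 0.025^(1/6) = 45.9%.

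**Exposure.** The zero count comes from 3 to 6 doses per subject, and Section 4.3 describes the initial regimen as about 2.5 billion cells per dose. The tolerability statement concerns up to 14 treatments of 5 billion cells. The limits in the 16 and 20 rows describe the earlier exposure only.

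**The case against.** The strongest reply has four parts.

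First, Phase 1 safety analysis is descriptive, no safety hypothesis or threshold is set, and anyone can derive an interval from a reported count and denominator. That is true, and it limits the severity. But an exact interval is itself descriptive and needs no hypothesis or extra subjects, and the plan already specifies one for a secondary endpoint.

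Second, Section 9.3 calls itself a summary and leaves detail to an SAP that would supersede it, and Section 9.3.1 allows limits where appropriate. This stands in part: an interval is not ruled out. It is simply not committed to for the primary endpoints, and the combined document holds no further SAP text that does so.

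Third, ongoing safety decisions rest on the DLT rules, the suspension triggers in Section 7.1 and DSMB review, and Table 1 in Section 2.3.1 still lists risks such as cytokine release syndrome and rates flu-like symptoms as medium risk. This also stands. A reader might infer that the plan concludes safety from an absence of events. Section 9.3.3 draws no such conclusion, and Section 4.3 is worded as a proposal, cites preclinical dosing and refers to DSMB review.

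Fourth, the figure near 20% is not the precision of the final AE analysis. A reader might carry it over to the primary AE and SAE results, but those use all dosed subjects, about 60 as planned, where an event-free result would leave rates up to 6.0% open. Likewise, a reader might expect a primary result of zero DLTs reported as 0%. The Section 9.2 definition would not produce that; it would produce 0/0.

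**Conclusion.** The point holds as a gap in planned reporting that should be closed. The primary safety incidences have no committed measure of uncertainty, the DLT incidence has neither a named analysis nor a usable denominator, and Sections 2.3.1 and 4.3 rest a tolerability statement on a zero count with no bound.

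The interim statement leaves related-event rates up to 20.6% open if n is 16 and 16.8% if n is 20. The 15 DLT-assessed subjects, if event-free, would leave 21.8% open. The interim range rests on an assumed n, which only the sponsor can replace with the actual number at the cut-off. Cohort sizes are not stated, so the width of by-cohort intervals cannot be given here. They will be wider than the overall ones when no events occur.

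None of these limits shows that the product is unsafe, and none speaks to the 5-billion-cell regimen.

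**What to change.** 1. **Section 9.2.** Redefine the DLT evaluable population as dosed subjects who either complete the DLT assessment period or have a DLT. This fits the replacement rule in Section 6.5 and has to come first, because no DLT interval can be computed until it is done. State at the same time whether the set is the first 15 subjects or the first 3 per cohort.
2. **Section 9.3.3.** Report the incidence of DLTs in that population, and of related Grade 3 or higher AEs, related SAEs and AEs leading to discontinuation in the Safety Analysis Set, each with a two-sided 95% Clopper-Pearson interval, overall and by cohort.
3. **Sections 2.3.1 and 4.3.** Replace the wording about an absence of related events with the count, the exact denominator at the cut-off, the exposure (3 to 6 doses, initial regimen about 2.5 billion cells per dose) and the upper limit. Add a sentence saying that this limit does not cover the 5-billion-cell regimen. No change of dose is proposed.

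The cost is a few more analysis lines, using a method the plan already specifies, and a stated safety figure that looks less favourable than a bare zero.

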#### **9.3.4 Other Analyses**

Additional details for pharmacodynamics and biomarker exploratory analyses will be described in the SAP finalized before database lock.

#### **9.3.5 Interim Analysis**

Open label study and no interim analysis is planned.

#### **9.3.6 Data Safety Monitoring Board (DSMB)**

The DSMB, a specific independent committee for the study with external representation composed of at least 3 members and include experts in the field of oncology and clinical studies, or biostatistics. Other members may be invited as needed. The DSMB will regularly monitor overall safety on an unblinded basis, as well as general aspects of study conduct, to ensure that the benefits and risks of study participation remain acceptable.

The DSMB will evaluate all relevant toxicity data and confirm that the principal investigator is reporting all serious, unexpected, or other related toxicities to the regulatory authorities.

During the conduct of the study, the DSMB will periodically be asked to advise the Sponsor regarding modification, continuation, or discontinuation of the study based on the review of the study safety data. Efficacy data will not be provided to the DSMB.

Details on the composition of the DSMB, meeting structure, schedule, and procedures, the content and format of DSMB reports, and other relevant details will be determined in consultation with DSMB members and detailed in a separate DSMB charter.

## **10 SUPPORTING DOCUMENTATION AND OPERATIONAL CONSIDERATIONS**

### **10.1 APPENDIX 1: REGULATORY, ETHICAL, AND STUDY OVERSIGHT CONSIDERATIONS**

#### **10.1.1 Regulatory and Ethical Considerations**

##### **10.1.1.1 Regulatory Requirements**

The Sponsor, Alloplex Australia Pty. Ltd., is the legal Australian Sponsor for the study and will fulfil the obligations that this role entails. The Sponsor shall, to the extent required by the applicable laws and regulations, interact with TGA in connection with this study. The planned regulatory pathway for this study is through the Clinical Trial Notification (CTN) scheme. Aside from approval by the HREC and notification of the TGA no other regulatory approval will be required.

##### **10.1.1.2 Ethical Conduct of the Study**

This study will be conducted in accordance with the principles of the current Declaration of Helsinki (Recommendations guiding Medical Doctors in Biomedical Research Involving Human Subjects) and with the NHMRC National Statement on Ethical Conduct in Research Involving Humans (2007, including current updates, 2018). The conduct of the study will be in accordance with the Integrated Addendum to International Council for Harmonisation (ICH) E6 (R1), Guideline for GCP E6 (R2) adopted by TGA (2000), annotated with comments by the TGA (2018).

This study will be conducted under a protocol reviewed and approved by an HREC at each site and investigations will be undertaken by scientifically and medically qualified persons, where the benefits of the study are in proportion to the risks. At each study site, the study will be overseen by an Investigator who, prior to study start at the site, will have read, and agreed understanding of the protocol requirements and will agree to conduct the study in accordance with the above.

##### **10.1.1.3 Ethics Review**

The final study protocol, including the final version of the PICF, must be approved, or given a favourable opinion in writing by an HREC as appropriate. The Investigator must submit written approval to the Sponsor before he or she can enrol any subject/subject into the study.

The Investigator is responsible for informing the HREC of any amendment to the protocol in accordance with local requirements. In addition, the HREC must approve all advertising used to recruit subjects for the study. The protocol must be re-approved by the HREC upon receipt of amendments and annually, as local regulations require.

The Investigator is also responsible for providing the HREC with reports of any reportable serious adverse drug reactions from any other study conducted with the study intervention. The Sponsor will provide this information to the Investigator.

Progress reports and notifications of serious adverse drug reactions will be provided to the HREC according to local regulations and guidelines.

#### 10.1.1.4 Sponsor and Investigator Obligations

##### Investigator Obligations

The Investigator and study staff are responsible for maintaining a comprehensive filing system of all study-related (essential) documentation. These include, but are not limited to: HREC correspondence, study intervention accountability logs, and curricula vitae of all personnel participating in the study. These files must be suitable for inspection at any time by the Sponsor, Clinical Research Associate, and/or applicable regulatory authorities.

##### Protocol Amendments

Neither the Investigator nor the Sponsor will modify or alter this protocol without the agreement of the other. All agreed protocol amendments will be clearly recorded on a protocol amendment form and will be signed and dated by the original protocol approving signatories. All protocol amendments will be submitted to the relevant HREC for approval before implementation, as required by local regulations. The only exception will be when the amendment is necessary to eliminate an immediate hazard to the study subjects. In this case, the necessary action will be taken first, with the relevant protocol amendment following shortly thereafter.

##### Protocol Deviations

Should any protocol deviation occur, it must be reported to the Clinical Research Associate (CRA) as soon as is reasonably practical. The deviation and the reason for its occurrence must be documented, reported to the relevant HREC (if required), and included in the study report.

#### 10.1.2 Financial Disclosure

Investigators and sub-Investigators will provide the Sponsor with sufficient, accurate financial information as requested to allow the Sponsor to submit complete and accurate financial certification or disclosure statements to the appropriate regulatory authorities. Investigators are responsible for providing information on financial interests during the study and for 1 year after completion of the study.

#### 10.1.3 Informed Consent Process

The Investigator(s) will ensure that the subject is given full and adequate oral and written information about the nature, purpose, possible risk, and benefit of the study. Subjects must also be notified that they are free to discontinue from the study at any time without prejudice. The subject should be given the opportunity to ask questions and allowed time to consider the information provided before voluntarily signing the written PICF.

The subject's signed and dated informed consent must be obtained before conducting any study procedures. The subjects will be informed of their rights to privacy but will be made aware that the study data will be submitted to the Sponsor and possibly to drug regulatory authorities for review and evaluation. They will be informed also that the CRA may inspect their medical records to verify the accuracy and completeness of the study records and results.

The acquisition of informed consent should be documented in the subject's medical records, as required by the Integrated Addendum to ICH E6(R1), GCP E6(R2), annotated with comments by the Australian Therapeutic Goods Administration (2018) and the NHMRC National Statement on Ethical Conduct in Human Research (2007, including current updates, 2018), and the PICF

will be signed and personally dated by the subject and by the person who conducted the informed consent discussion (not necessarily an Investigator).

The Investigator must maintain the original, signed PICF. A copy of the signed PICF must be given to the subject or legal representative. The date that informed consent was signed will be recorded on the eCRF.

#### **10.1.4 Data Protection**

- Subjects will be assigned a unique identifier by the Sponsor. Any subject records or datasets that are transferred to the Sponsor will contain the identifier only; subject names or any information which would make the subject identifiable will not be transferred.
- The subject must be informed that his/her personal study-related data will be used by the Sponsor in accordance with local data protection law. The level of disclosure must also be explained to the subject who will be required to give consent for their data to be used as described in the informed consent
- The subject must be informed that his/her medical records may be examined by Clinical Quality Assurance auditors or other authorized personnel appointed by the Sponsor, by appropriate HREC members, and by inspectors from regulatory authorities.

